### **Design**

We adopted a randomized crossover design and divided the participants into a caffeine trial (CAF) and placebo trial (PL). The order of the trials in a test was randomized, and tests were separated by 7 days to avoid interference. At least 1 week before the formal experiment, all participants participated in three to five familiarization tests, such as cognitive function tests and shooting tests. The primary outcome was cognitive function, and the secondary outcome was shooting performance.

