### **Outcome measure**

The color–word Stroop task and visual search test were conducted using Psych/Lab for Windows. Measures used in the literature with satisfactory reliability and validity were adopted. The Stroop task involved four base colors, namely red, green, blue, and yellow, and the names of the base colors were presented in Chinese characters and in various colors to confuse the participants. The participants were required to press a key corresponding to the base color name they saw on screen (“R” for red, “G” for green, “B” for blue, and “Y” for yellow). In each test, 80 trials lasting 5 min each were conducted. The test results comprised a congruent condition, in which the key pressed corresponded correctly to the color on screen, and an incongruent condition, in which the key pressed corresponded incorrectly to the color name on screen.

In the visual search test, participants identified orange “T”s on the screen from upside-down orange “T”s, blue “T”s, and upside-down blue “T”s. When an orange “T” would appear, the participants were required to press the space bar as quickly as possible. If no orange “T” appeared, the participants were required to not react. A total of 80 search displays were presented in 5 min. In each display, 5, 10, 15, or 20 -Ts were presented.

The shooting ability test involved a three-dimensional aim trainer, which was proposed in a previous study [12]. Participants used the mouse to shoot the electronic targets on the computer screen. The test comprised 60 targets and could be completed in 2 min. It was performed on a static map with medium difficulty. In each round, three targets appeared at once, and participants were required to shoot them within 2 s, ideally eliminating each target with a one-shot kill. Participants’ kill ratio (number of targets

hit/60), hit accuracy (60/number of shooting), and average time to target were noted.

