### **Statistics**

All data are presented as averages  $\pm$  standard deviations. The Shapiro–Wilk test was used to examine the normality of the data. Cognitive performance, accuracy, and hit reaction time were analyzed through a paired sample t test. We used G\*power 3 software to achieve an alpha value of 5% and a power of 0.8; a sample of six was considered sufficient for this study. All data were calculated using SPSS (version 20, Chicago, IL, USA), and the significance level was  $\alpha < 0.05$ .

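### Hit accuracy is defined with a fixed numerator of 60 instead of targets hit, so it overstates hits per shot by a factor of 1/kill ratio whenever a target is missed

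*Protocol*

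**What the plan says.** The Outcome measure section describes the shooting test: "The test comprised 60 targets and could be completed in 2 min". On the rounds it says: "In each round, three targets appeared at once, and participants were required to shoot them within 2 s". Three results are recorded. The first is "kill ratio (number of targets", and the sentence continues "hit/60), hit accuracy (60/number of shooting), and average time to target were noted". The definition at issue is the second of these, "hit accuracy (60/number of shooting"). In symbols, with h targets hit and s shots fired, kill ratio is h/60 and hit accuracy is 60/s.

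The Design section sets the role of these measures: "The primary outcome was cognitive function, and the secondary outcome was shooting performance". The Statistics section gives the analysis: "Cognitive performance, accuracy, and hit reaction time were analyzed through a paired sample t test". It does not say which accuracy is meant. Accuracy is listed apart from cognitive performance and next to hit reaction time, so shooting accuracy is the natural reading.

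**The concern.** A measure called hit accuracy should say what share of the shots hit a target. The stated formula divides the number of targets offered by the number of shots, so it depends only on how many shots were fired. Someone who fires 60 shots scores 100% whether 60 targets were hit or 30.

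This would be harmless if every target were always hit. The protocol does not say so. It sets a 2 s limit on each round of three targets and records kill ratio as a result of its own, which would be a constant 1 if no target could be missed.

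At stake is a component of the secondary outcome. If the formula was applied as written, a participant who hits more targets with somewhat more shots can be scored as less accurate, and the paired comparison of caffeine with placebo can point the wrong way.

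**Working it through.** **Inputs from the protocol (Outcome measure section).** Targets presented: 60. Kill ratio: K = h/60. Stated hit accuracy: 60/s. The protocol reports no values of h or s, so every count below is assumed for illustration. Accuracy here means targets hit per shot, h/s.

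**Step 1: relation between the two formulas.**

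(60/s) ÷ (h/s) = 60/h = 1/K, whatever the value of s.

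The two agree only at h = 60. The factor is 1/0.98 = 1.020, 1/0.95 = 1.053, 1/0.90 = 1.111 and 1/0.75 = 1.333.

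**Step 2: range.** The stated measure exceeds 1 whenever s < 60. With h = 48 and s = 50 it gives 60/50 = 1.20, while targets hit per shot is 48/50 = 0.96.

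**Step 3: effect on a within-person difference.** Let session 1 have (h1, s1) and session 2 have (h2, s2).

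- If h1 = h2, both scores are multiplied by the same 1/K. The direction is kept, but the size of the difference is inflated by 1/K.
- If h1 ≠ h2, the factors differ and the error does not cancel. True accuracy rises when h2/h1 > s2/s1. The stated measure rises only when s2 < s1. The sign is therefore reversed for a true rise when 1 < s2/s1 < h2/h1, and for a true fall when h2/h1 < s2/s1 < 1. In words, shots move in the same direction as hits but by a smaller proportion.

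**Step 4: assumed pairs.**

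| Pair | Placebo h/s | Caffeine h/s | True accuracy | True change (points) | As stated (60/s) | Stated change (points) |
|---|---|---|---|---|---|---|
| Near the ceiling | 57/70 | 59/72 | 81.4% v 81.9% | +0.5 | 85.7% v 83.3% | −2.4 |
| Large change in kill ratio | 45/65 | 57/70 | 69.2% v 81.4% | +12.2 | 92.3% v 85.7% | −6.6 |
| True null | 45/50 | 54/60 | 90.0% v 90.0% | 0 | 120.0% v 100.0% | −20.0 |

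The first two pairs meet the reversal condition. Near the ceiling, s2/s1 = 72/70 = 1.029 and h2/h1 = 59/57 = 1.035. For the large change, 70/65 = 1.077 and 57/45 = 1.267. In the third pair both ratios equal 1.20, so nothing changed in truth, yet the stated measure shows a loss.

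**Step 5: recovery.** K × stated hit accuracy = (h/60) × (60/s) = h/s. If the fixed 60 was used, the two recorded results give the intended measure exactly.

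**The case against.** The strongest reply is that this is probably a slip of the pen. The test is taken from a previous study, the wording is loose, and the data may well have been scored as hits over shots. This stands in part: the definition is wrong as written, but bias in the results follows only if the fixed 60 was used in scoring, which the protocol does not settle.

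The second reply concerns size. The players are nationally placed, had three to five familiarization tests, and shot on a static map of medium difficulty, so kill ratios may be near 1. Nothing in the protocol supports a kill ratio of 0.75, as assumed in the last two pairs. At 0.95 to 0.98 the inflation is only 2% to 5%, and the reversal window in the near-ceiling pair is narrow (1.029 against 1.035). This also stands: sign reversal is possible, but the protocol gives no ground for calling it likely.

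The third reply is that a kill need not take exactly one shot on target, since the text says "participants were required to shoot them within 2 s, ideally eliminating each target with a one-shot kill". If a target can absorb several hits, the overstatement of total hits per shot is 60/(total hits), not 1/K. With accuracy defined as targets hit per shot, the factor and the recovery formula still hold. Under either definition, 60/s is not an accuracy unless its numerator happens to equal the hits.

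Reading the test as one in which all 60 targets are always hit would rescue the formula, but it would leave kill ratio with nothing to measure.

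**Conclusion.** The concern holds. As written, hit accuracy is the reciprocal of shots fired times a constant. It equals targets hit per shot only when all 60 targets are hit and is otherwise too high by exactly 1/kill ratio. It can exceed 100%, and it can reverse a paired difference when the kill ratio differs between caffeine and placebo. No other statement in the protocol corrects it.

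The identity is certain. The size in this trial is not, because it depends on hit and shot counts that are not given and on whether the fixed 60 was used in scoring. That accuracy in the Statistics section means hit accuracy is a fair inference, not a stated fact. The scope is one of three shooting measures in the secondary outcome. The primary cognitive outcome, kill ratio, time to target and the sample size are unaffected. The definition should be fixed, but it does not threaten the trial's main question.

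**What to change.** - In the Outcome measure section, define hit accuracy as number of targets hit divided by number of shots fired. Keep kill ratio (targets hit over 60) as the separate completion measure.
- Check which formula was applied to the recorded data. If it was already hits over shots, correct the text only and leave the data alone; multiplying by kill ratio would then introduce an error.
- If the fixed 60 was used, recompute each participant's value in each session as kill ratio × recorded hit accuracy, then rerun the paired comparison.
- Name hit accuracy explicitly in the Statistics section.

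The cost is one formula, one check of the scoring and, at most, one recomputation. Both quantities needed are already recorded, so no new data are required.

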### **Statistics**

All data are presented as averages  $\pm$  standard deviations. The Shapiro–Wilk test was used to examine the normality of the data. Cognitive performance, accuracy, and hit reaction time were analyzed through a paired sample t test. We used G\*power 3 software to achieve an alpha value of 5% and a power of 0.8; a sample of six was considered sufficient for this study. All data were calculated using SPSS (version 20, Chicago, IL, USA), and the significance level was  $\alpha < 0.05$ .

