## **Methods**

### **Participants**

We recruited nine healthy male adults (with the desired age and training). All participants had experience with national competitions and regularly underwent training in first-person shooters. They consumed less than 80 mg of caffeine a day and did not have any diseases affecting the heart, bones, and joints or diseases that preclude exercise. Before the experiment, all participants were fully informed of the experimental procedures and the possible risks, and they provided informed consent. This study received approval from the Institutional Review Board of Jen-Ai Hospital – Dali Branch (110-06). This study was conducted in accordance with the Declaration of Helsinki.

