### **Experimental procedure**

All tests were conducted in a professional e-sports classroom, and the indoor ambient temperature was set at 26°C. Participants' diet and meal times were recorded for the 3 days before the first experiment, and the participants were required to follow the same diet 3 days before the subsequent experiment. They were also required to

avoid food and beverages with caffeine (e.g., coffee, energy drinks, chocolate, and tea) during this period.

On the day of the formal experiment, participants had breakfast and lunch at 8:00 a.m. and 12:00 p.m., respectively, and arrived at the classroom at approximately 3:00 p.m. for the experiment. The participants took capsules with 3 mg/kg of caffeine (the CAFtrial) or a placebo capsule (the PLtrial) with 200 mL of water. The placebo capsule contained flour. Each participant had a computer with a frame rate of at least 240 Hz and a mouse of scrolling speed of 1 ms. After the participants remained in the room for 1 hour, during which they were required to take a rest in any form of their choosing except engaging in esports, the Stroop task, visual search test, and shooting ability test were conducted.

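### The two-period crossover in nine players is analysed by a paired t test with no period term; reporting the order split and a period-adjusted estimate is a minor, cheap improvement

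*Protocol*

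**What the plan says.** The protocol's Participants section states "We recruited nine healthy male adults". Under Design, each player takes caffeine (CAF) on one test day and placebo (PL) on the other: "The order of the trials in a test was randomized, and tests were separated by 7 days to avoid interference". No method of randomization and no number of players per order is given.

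The Statistics section then names the analysis: "Cognitive performance, accuracy, and hit reaction time were analyzed through a paired sample t test". The protocol mentions no period term, no restriction on the orders and no check for an order effect. On sample size it says only that "a sample of six was considered sufficient for this study", with 5% alpha and power 0.8.

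Several features act against a difference between the two visits. Before the experiment "all participants participated in three to five familiarization tests, such as cognitive function tests and shooting tests". On experience: "All participants had experience with national competitions and regularly underwent training in first-person shooters". On diet, "the participants were required to follow the same diet 3 days before the subsequent experiment", and meal and arrival times are set.

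**The concern.** The outcomes are repeated computer tasks (Stroop, visual search, aiming), where a second visit may go better or worse than the first regardless of capsule. A paired t test averages the CAF minus PL differences over all players. That average cancels a period effect only when the two orders are equally frequent, which nine analysed players cannot achieve. Part of any period effect is then credited to caffeine or subtracted from it, depending on which order was commoner. The period effect also adds spread to the differences, because it enters with opposite sign in the two orders. The seven-day gap is aimed at carry-over of one test into the next; it does not remove a general difference between visits.

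**Working it through.** **The plan's own figure.** A sample of six cannot be reproduced because no effect size or sidedness is stated. For a paired t test at 5% alpha and 80% power, six players correspond to an effect of 1.43 SD of the differences (two-sided) or 1.19 SD (one-sided). Nine players have 80% power, two-sided, at 1.07 SD. These three values are used below as assumed effects.

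**Inputs.** n = 9 (Participants); two periods in randomized order (Design); paired t test (Statistics). Assumed: the period effect p, in units of the SD of the differences among players with the same order, and the split.

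**Shift.** With true effect t, the expected CAF minus PL difference is t − p for a CAF-first player and t + p for a PL-first player. The mean over nine is

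t + p × (n PL-first − n CAF-first)/9.

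The numerator is odd, so with nine analysed the multiplier of p is at least 1/9 in size.

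**Spread.** With a and b players in the two orders, the expected variance of the differences is multiplied by 1 + p² × 4ab/72. At 5:4 and p = 0.5 this is 1 + 0.25 × 80/72 = 1.278, so the standard error rises by about 13% (√1.278 = 1.13).

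**Adjusted analysis.** Average the two order-specific mean differences. Then p cancels, the standard error is √((1/a + 1/b)/4) SD, and 7 degrees of freedom remain instead of 8.

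**Results by split** (simulation with normal differences, two-sided 5%; chance of each split if orders were set by coin flip, an assumption):

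| Split | Chance | Size of shift | Paired type I error, p = 0.5 | Adjusted power at 1.07 SD, p = 0 (paired 0.80) |
|---|---|---|---|---|
| 5:4 | 0.492 | p/9 | 0.032 | 0.78 |
| 6:3 | 0.328 | p/3 | 0.05 | 0.74 |
| 7:2 | 0.141 | 5p/9 | 0.086 | 0.63 |
| 8:1 | 0.035 | 7p/9 | 0.15 | 0.41 |
| 9:0 | 0.004 | p | 0.26 | not estimable |

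**At 5:4 in more detail** (p in the direction of the caffeine effect):

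- p = 0.25: the shift is 0.25/9 = 0.028 SD. Mean confidence-interval width is 1.54 SD paired against 1.53 adjusted, and power at 1.07 SD, averaged over the two directions, is 0.78 for both.
- p = 0.5: the shift is 0.056 SD and the widths are 1.69 against 1.53. Paired power with five CAF-first or five PL-first, against adjusted power, is 0.67 or 0.76 v 0.78 (effect 1.07 SD), 0.77 or 0.84 v 0.86 (1.19 SD), and 0.91 or 0.95 v 0.95 (1.43 SD).
- Mean squared error is equal at p = √((0.1125 − 0.1111)/(1/9)²) = 0.34.

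**Averaged over coin-flip allocation**, paired type I error is 0.050, 0.050, 0.050 and 0.052 at p = 0, 0.25, 0.5 and 1. Average power at 1.07 SD, paired against always adjusted (9:0 counted as no rejection), is 0.80 v 0.73, 0.78 v 0.73, 0.71 v 0.73 and 0.50 v 0.73.

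**The case against.** The strongest defence is that paired analysis of a randomized crossover is sound on average and that nothing shows a period effect here. Familiarization, experienced players, repeated diet and fixed times all make a large p less likely. Over fair randomization the shift averages to zero and type I error stays near 0.05. With nine players a degree of freedom matters, and with coin-flip orders always adjusting has less average power at 1.07 SD until p is about 0.45 SD. At 7:2 the adjusted interval is still wider than the paired one at p = 0.5 (1.83 against 1.63 SD). All of this stands, and it keeps the point minor.

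It does not remove the point. The trial has one realised split, and the average over splits that did not occur does not tell a reader how far this estimate may have moved. Some of the paired test's power at unequal splits is period effect credited to caffeine, and its interval there is off-centre. Familiarization varied in number and ended at least a week before the experiment, so it lowers p without showing that p is zero. The analysis plan is not at hand and may add a period term, but the protocol itself names the paired test.

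A reader might infer that the caffeine effect is biased by at least a ninth of its own size. The documents do not support that: the ninth is of the period effect, whose size is unknown. It also holds only if all nine are analysed; one dropout could leave 4:4 and no shift.

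**Conclusion.** The point holds as a minor improvement. The stated analysis leaves any residual period effect in the caffeine estimate, in proportion to the imbalance in order, and offers no way to see it. At 5:4 with p of 0.25 SD or less the consequence is negligible. At 5:4 with p of 0.5 SD the main cost is precision: an interval about 10% wider (1.69/1.53) and a conservative test. Larger distortion needs both a real period effect and a split of 7:2 or worse.

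A reader might conclude that the trial has an inflated false-positive rate. That is not shown: it arises only at very uneven splits with an appreciable p, and averaged over fair allocation the error rate stays at about 0.05. The figures rest on assumed values of p and of the effect, normal differences, all nine players analysed and, for the averages, coin-flip orders.

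**What to change.** In the Statistics section, report the number of players in each order. Whenever both orders are present, including at 8:1, give for each outcome the period-adjusted caffeine effect from a linear model with treatment, period and participant (7 degrees of freedom).

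- If this is specified before the data are seen, make it the main analysis.
- Otherwise keep the stated paired t test as the main analysis and add the adjusted estimate, labelled as a sensitivity analysis. The protocol is written in the past tense, so this may be the applicable case.
- Do not choose the test according to the realised split. Reverting to the paired test at 8:1 would use it where it is badly distorted (type I error 0.15 at p = 0.5 SD, against 0.05 adjusted). At 9:0, state that period and treatment cannot be separated.
- If allocation is still open, restrict the orders to 5:4.

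Cost as the main analysis: one degree of freedom and, with no period effect, the power losses in the table (0.80 to 0.78 at 5:4, but 0.63 at 7:2 and 0.41 at 8:1, for an assumed 1.07 SD effect). Cost as a sensitivity analysis: a little more analysis work. Either way each player's order must have been recorded, which the protocol does not state.

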## **Introduction**

Owing to the popularity of e-sports, numerous countries have recognized e-sports as a formal sport. E-sports were also included as a demonstration event at the 2018 Asian Games in Jakarta. Professional e-sports leagues have been founded in several countries. E-sports include multiplayer online battle field arena games (e.g., *League of Legends*), first-person shooter games (e.g., *Counter-Strike: Global Offensive*, and *Valorant*), real-time strategy games, and sports games (1). Studies on first-person shooters have revealed that players with experience in competitions had shorter reaction times in a Stroop test (2) and stronger visual search abilities (3). Therefore, improving cognitive abilities that relate to e-sports competitions may be critical for participants in first-person shooter competitions, and external nutrients that enhance cognitive abilities may be crucial to their success.

Caffeine is a popular and effective ergogenic supplementation for athletes of all levels (4, 5). It is typically consumed through food and drink, and the mechanism through which low-dose caffeine acts as a psychostimulant is based on central antagonism at the A1 and A2A adenosine receptors. The capacity of caffeine to bind adenosine receptors facilitates the inhibition of the brake that endogenous adenosine imposes on the ascending dopamine and arousal systems, which facilitates cholinergic and dopaminergic transmission (6, 7). Therefore, caffeine consumption may improve energy, mood, cognitive function, attention, simple reaction time, choice reaction time, and memory and alleviate fatigue (8, 9). The consumption of caffeine 1 hour before playing a first-person shooter can improve players' visual search ability and speed in a state of alertness (10). A dosage of 3 mg/kg of caffeine before a game can increase

players' typing speed (11), shorten their reaction times, and increase their shooting accuracy (12). However, few studies have explored this.

Because visual search ability and the presence of decoys, which can distract players, can both affect play performance in first-person shooters, reaction time alone is insufficient as an index for cognitive ability in research on the effect of caffeine on shooting accuracy. We explored the effect of caffeine ingested 1 hour before a first-person shooter on players' performance by using a Stroop task and testing the players' visual search and shooting abilities.

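### Does the unsupported statement that six participants suffice make the trial's sample size, or its reading of a null cognitive result, unsound?

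*Protocol*

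**What the plan says.** The Statistics section states that G*Power 3 was used with an alpha of 5% and "a power of 0.8; a sample of six was considered sufficient for this study". On the analysis it says "Cognitive performance, accuracy, and hit reaction time were analyzed through a paired sample t test". On presentation it says "All data are presented as averages", accompanied by standard deviations.

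The Participants section says "We recruited nine healthy male adults", so enrolment exceeds the stated need by three. The Design section describes a randomized crossover in which each player is his own control, and says "The primary outcome was cognitive function, and the secondary outcome was shooting performance". The Outcome measure section shows that the cognitive part consists of a Stroop task with two conditions and a visual search test.

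The Introduction gives a direction for the expected effect but no size. It says "caffeine consumption may improve energy, mood, cognitive function, attention" and, of work in players, "However, few studies have explored this".

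**The concern.** Power is always power against a particular difference. The protocol states the alpha, the power, the software and the answer, but leaves out the one input that gives the answer meaning. It also does not say which cognitive measure was used, or whether the test was one- or two-sided.

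Worked backwards, six looks demanding. With normally distributed differences, a mean shift of 1.43 SD of the differences implies that about 92 of 100 players do better on caffeine (88 of 100 at the one-sided 1.19). Nothing in the Introduction supports a figure of that kind for a cognitive measure.

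What would be at stake is the reading of a null primary result. If the true shift were smaller, say 0.5 to 1.0 SD, nine players would often miss it. A reader who took the word sufficient at face value might then conclude that caffeine does nothing. The stated outputs would not warn that reader, because averages and SDs by condition do not give the SD of the paired differences and so do not yield an interval for the effect.

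**Working it through.** **Inputs from the protocol.** Alpha 5%, power 0.8, paired t test, six stated as sufficient (all Statistics); nine recruited (Participants); crossover (Design). Not stated: mean difference, SD of differences, sidedness, the variable, and the test selected in G*Power. I assume it was the paired t test named for the analysis, and show both one- and two-sided results.

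**The plan's own figure.** Six cannot be reproduced forwards because no effect is given. It can only be inverted. Let dz be the mean difference divided by the SD of the within-person differences. The test statistic follows a noncentral t with n − 1 degrees of freedom and noncentrality dz × √n, and two-sided power is the probability that it falls beyond ± t(0.975, n − 1). Solving for 80% power:

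| n | dz, two-sided | dz, one-sided |
|---|---|---|
| 5 | 1.682 | 1.359 |
| 6 | 1.435 | 1.186 |
| 9 | 1.067 | 0.909 |

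Six is therefore the smallest adequate number if the planners entered a dz from 1.435 up to 1.682 two-sided, or from 1.186 up to 1.359 one-sided. Any such input makes the statement arithmetically correct. Simulation with 1,000,000 trials at dz = 1.435 and n = 6 gave power 0.800.

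**Share of players improving under normality.** Φ(1.435) = 0.924; Φ(1.186) = 0.882.

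**Two-sided power for a range of true effects.** The values 0.5 to 1.0 are assumptions; the protocol gives none.

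| dz | power, n = 6 | power, n = 9 | pairs needed for 80% |
|---|---|---|---|
| 0.5 | 17% | 26% | 34 |
| 0.8 | 36% | 56% | 15 |
| 1.0 | 51% | 75% | 10 |
| 1.435 | 80% | 96% | 6 |

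**Interval width.** The 95% half-width is t(0.975, n − 1)/√n in observed SDs of the differences. For n = 9 it is 2.306/3 = 0.769; for n = 6 it is 2.571/2.449 = 1.05. A zero estimate with nine thus leaves about ±0.77 SD inside the interval.

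**Is 1.435 implausibly large?** With equal SDs in the two conditions and within-person correlation ρ (assumed), the effect in between-person SDs is dz × √(2(1 − ρ)):

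- ρ = 0.5: 1.435 × 1.000 = 1.435
- ρ = 0.8: 1.435 × 0.632 = 0.91
- ρ = 0.9: 1.435 × 0.447 = 0.64

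The same required dz covers a wide range of effects on the ordinary scale. The protocol takes steps that should raise ρ: three to five familiarization tests, a repeated three-day diet and fixed meal times, and 80 trials or displays in each cognitive test.

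**The case for a change.** The best case for a change is that the protocol chose to make a sample-size claim. An incomplete claim of that kind is a fault of this document, not something deferred to an SAP. The cure is cheap: a few sentences giving the G*Power inputs or, if these are lost, the effect detectable with nine, plus a confidence interval for each paired difference. No new data would be needed. Recruiting nine does not remove the problem, since 1.07 SD is still required and moderate effects cannot be excluded.

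Much of this stands. The inputs are absent, the thresholds are right, and a null result from nine players would be weak evidence against effects well below 1.07 SD. An interval for the paired difference would be a helpful addition to the report.

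Three parts do not stand.

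- The consequence depends on someone reading a null result as no effect, and the protocol contains no such rule. Added wording would guard against a conclusion that the plan does not draw.
- Calling the implied effect very large goes further than the document allows, because the within-person correlation is unknown. Nothing in the protocol makes 0.5 to 1.0 SD more likely than 1.43. If 1.43 were true, nine players would have 96% power, so a null result would be informative about an effect of that size.
- Stating averages with SDs as the way data are presented does not rule out intervals. Which estimates are tabulated is commonly settled in an SAP, which may exist here and has not been seen.

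**Conclusion.** The sample-size sentence is under-documented, but it is not shown to be wrong, and nothing in the design or analysis needs to change. On the assumption that the calculation was for the planned paired t test, six is adequate for a mean difference of at least 1.43 SD of the within-person differences (1.19 one-sided), and the nine recruited for at least 1.07 (0.91). No stated power is shown to be missed. Enrolment was 9/6 = 1.5 times the stated need.

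Stating the inputs would alter neither the participants, the test nor the p-values. An analyst with the paired data can compute the interval directly, and a careful reader will treat a null result from nine as leaving moderate effects open, with a 95% half-width of about 0.77 observed SD. Whether effects of this order are plausible cannot be settled from the protocol, because that turns on an unstated correlation.

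The software citation numbered 24, in a reference list that ends at 12, is a clerical slip with no bearing on the result.
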